# **BACKGROUND**

# Study Purpose and Rationale:

Ureteral stents treat ureteral obstruction, allow for passive dilation of the ureter, maintain urine flow to the bladder, and aid in the recovery of the ureter after endoscopic surgery or ureteral injury. These stents are routinely utilized after urologic procedures for the treatment of urolithiasis and are generally kept in place for 1-2 weeks following the procedure. Despite their advantages, indwelling ureteral stents cause discomfort and reduce patient quality of life. These symptoms are partially attributed to local irritation to the ureter and bladder. Bothersome stent-related symptoms include urinary urgency, frequency, flank pain, hematuria, dysuria, sexual side effects, and emotional distress. The majority of patients with ureteral stents experience symptoms postoperatively. Several studies have indicated that agents such as antimuscarinics or alpha-1 adrenergic receptor antagonists may improve stent-related symptoms. The indications for anticholinergic medications are based on blocking involuntary bladder muscle contraction; however, the efficacy of these drugs is still controversial. Furthermore, these medications have potential adverse side effects. Antihistamines also show potential in alleviating stent-related symptoms. Multiple in vitro studies have shown H1 receptor activity involved both in ureteral peristalsis and in bladder contraction. Both first- and second-generation H1 antagonists have shown activity in the urinary tract. In clinical practice, antihistamines are commonly utilized in the management of bladder pain caused by interstitial cystitis. Additionally, a randomized controlled trial found efficacy of antihistamines for pain management in the setting of renal colic from obstructing ureteral stones. There is novel evidence that in patients with indwelling stents, there are inflammatory changes in the bladder with an associated eosinophilic reaction. Eosinophilic cystitis is commonly associated with bladder irritation or allergy, and these findings point to a novel paradigm of treating patients with antihistamines. To our knowledge, no studies have evaluated the efficacy of antihistamines for managing stent-related symptoms. We propose a randomized controlled trial to evaluate the efficacy of antihistamines in improving symptoms in patients with indwelling ureteral stents.

#### Research Aims & Abstracts:

Ureteral stents are routinely utilized after urologic procedures for the treatment of urolithiasis. Despite their advantages, indwelling ureteral stents cause discomfort and reduce

patient quality of life. Antihistamines show potential in alleviating stent-related symptoms. To our knowledge, no studies have evaluated the efficacy of antihistamines for managing stent-related symptoms. We propose a randomized controlled trial to evaluate the efficacy of antihistamines in improving symptoms in patients with indwelling ureteral stents.

We propose a prospective, double-blind, randomized, open label, single-center trial. 78 patients will be enrolled. Eligible participants will be adult patients (aged 18–80 years) who are undergoing unilateral retrograde ureteroscopy with planned ureteral stent placement for treatment of urinary tract stones. Eligible patients will be randomly divided into two groups in a 1:1 ratio. Group A will receive fexofenadine 180 mg once daily in addition to standard of care treatment. Group B will receive placebo in addition to standard of care treatment. The routine standard of care treatment will consist of oral NSAIDs. Results: The primary outcomes of the study are the Ureteral Stent Symptom Questionnaire (USSQ) urinary symptom score and pain score. Secondary outcomes include (i) number of office phone calls due to urinary symptoms; (ii) duration of analgesic use; (iii) duration and quantity of narcotic use; (iv) number of emergency department visits; (v) drug-related adverse effects; (vi) other domains of the USSQ.

# STUDY DESIGN

We propose a prospective, double-blind, randomized, placebo-controlled, single-center trial. 78 patients will be enrolled. All patients will be provided written and informed consent. Eligible participants will be adult patients (aged 18–80 years) who are undergoing unilateral retrograde ureteroscopy with planned ureteral stent placement for treatment of urinary tract stones. The exclusion criteria are as follows: (i) preoperative use of antihistamines, beta-3 agonists, anticholinergics, corticosteroids, and chronic opioid analgesic use; (ii) preoperative indwelling ureteral stent at the time of treatment; (iii) neurogenic bladder, ureteral stricture, interstitial cystitis, or chronic prostatitis; (iv) pregnancy or breastfeeding; (v) planned bilateral ureteroscopy; (vi) solitary or transplanted kidney; (vii) hypersensitivity to antihistamines; (viii) severe renal disease (GFR < 10 ml/min or on dialysis). All patients will provide written, informed consent preoperatively. Unilateral ureteroscopic stone removal surgery will be performed under general anesthesia with a semirigid and/or flexible ureteroscope. At the conclusion of lithotripsy, a silicone double pigtail ureteral stent will be placed. Size and length of the stent will be at the discretion of the treating urologist. Patients will be excluded and will not be randomized if: (i) a ureteral stent

is not deemed necessary; (ii) there is a significant deviation in the operative plan involving a urologic malignancy or tandem stent placement (two stents in one ureter); (iii) a second-stage procedure for further stone treatment is required.

Following surgery, eligible patients will be randomized into one of two groups in a 1:1 ratio using varying block sizes. The randomization table will be built by a biostatistician and sent directly to the pharmacy who will be responsible for treatment allocation. The patients and the treating urologist will both be blinded to the treatment allocation. Group A will receive fexofenadine 180 mg once daily in addition to standard of care treatment. Group B will receive placebo in addition to standard of care treatment. The study drug will be taken starting on the evening of surgery (post-operative day #0) and will continue until the stent is removed. The routine postoperative standard of care treatment will consist of oral non-steroidal anti-inflammatory agents (NSAIDs). This treatment will be modified as needed on an individualized basis based on contraindications to these medications. If patients require further pain medication, narcotics will be considered on a limited basis depending on individual patient requirement, as per the standard of care, and the amount used will be tracked. Patients will be asked to keep a record of their analgesic usage. Anticholinergic medications may also be prescribed in the postoperative period for patients with significant bother by urinary urgency and frequency. If these medications are prescribed, their usage will also be tracked. Alpha blockers will not be prescribed routinely, but they will be continued in patients who take them chronically. The timing of ureteral stent removal will be determined based on physician and patient preference and will routinely be 1-2 weeks after surgery.

All patients will complete the Ureteral Stent Symptom Questionnaire (USSQ) three times: at their preoperative office visit, at the time of stent removal, and at their follow-up visit after stent removal. At the time of stent removal, patients will also report their usage of NSAIDs, anticholinergics, and narcotics. Patients will also be asked about drug-related adverse effects. The clinical research coordinator will contact patients every 2-3 days to assess for side effects, to maintain compliance to protocol, and to ensure patients are maintaining medication logs.

The primary outcomes of the study are the USSQ urinary symptom score and pain score. Secondary outcomes include (i) number of office phone calls due to urinary symptoms and pain; (ii) duration of NSAID use; (iii) duration and quantity of narcotic use; (iv) number of emergency department visits; (v) drug-related adverse effects; (vi) other domains of the USSQ.

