# STATISTICAL PROCEDURES

Sample size calculations were determined based on a previous meta-analysis investigating the effect of alpha-antagonists in reducing ureteral stent-related discomfort (Lamb et al, BJU Int, 2011). This study included five randomized controlled trials, four of which were placebo controlled. The study found a difference of 8.4 points in the Ureteral Stent Symptom Questionnaire (USSQ) urinary symptom score (mean 20.0, SD 5.6 vs. mean 28.4, SD 6.2) and a difference of 7.2 points in the USSQ pain score (mean 11.9, SD 10.1 vs. mean 19.1, SD 10.9) in the treatment group compared to the control group. Assuming a similar treatment effect, a t-test with a two-sided significance level of 0.05 will require a sample size of 35 patients in each group to detect a difference in the pain score between the two groups with a power of 80%. A sample size of 35 is larger than required to detect a difference in the urinary symptom score with the same power. Assuming a drop-out rate of 10%, 39 patients per group will be randomized.

To compare outcomes, t-tests will be used for continuous variables, and chi-square tests will be used for nominal variables. Statistical analyses will be performed using Stata (Statacorp, College Station, TX, USA). Power and sample size calculation was performed using G\*Power 3.1 (Dusseldorf, Germany).

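### Does enrolling 78 patients before surgery leave too few to randomise 39 per group?

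*Combined protocol and SAP*

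**What the plan says.** The Study Design section states that "78 patients will be enrolled"; the abstract under Research Aims & Abstracts gives the same number. On timing, Study Design says "All patients will provide written, informed consent preoperatively", and the first USSQ is completed at the preoperative office visit. The section then lists findings at surgery that stop a patient going further, beginning "Patients will be excluded and will not be randomized if: (i) a ureteral stent" (not needed). The other two are a significant deviation in the operative plan (urologic malignancy or tandem stents) and the need for a second-stage procedure. Randomisation comes after this: "Following surgery, eligible patients will be randomized into one of two groups in a 1:1 ratio using varying block sizes".

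Statistical Procedures derives 35 per group from the pain score and ends: "Assuming a drop-out rate of 10%, 39 patients per group will be randomized". That is 78 randomised in total. The protocol does not define enrolment, give an expected rate of exclusion at surgery, or state a replacement rule.

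**The concern.** The same number, 78, is attached to two stages that patients reach at different times, and the protocol itself provides for losses between them. If a patient counts as enrolled on signing consent, 78 enrolled and 78 randomised can both be true only if nobody is excluded at surgery, yet three reasons for such exclusion are written in. The 10% allowance does not help, because it is spent on loss after randomisation. If accrual stopped at 78 consents, the trial could finish with fewer than 35 evaluable patients per group. Pain is a primary outcome and the one that set the sample size, and its calculation has almost no slack.

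**Working it through.** **Inputs from Statistical Procedures.** Pain: difference 7.2, SDs 10.1 and 10.9. Urinary symptoms: difference 28.4 − 20.0 = 8.4, SDs 5.6 and 6.2. Two-sided t-test at 0.05, target power 80%, drop-out 10%, 1:1 allocation.

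**Reproducing the plan's figures.**
- Pain SD = √((10.1² + 10.9²)/2) = 10.51, so d = 7.2/10.51 = 0.685.
- Power from the noncentral t distribution, with noncentrality 0.685 × √(n/2) and 2n − 2 degrees of freedom: n = 34 gives 79.5%; n = 35 gives 80.7%. The first n to reach 80% is 35, as stated.
- Drop-out: 35/0.9 = 38.9, rounded up to 39; 2 × 39 = 78, as stated.
- Urinary SD = √((5.6² + 6.2²)/2) = 5.91. Nine per group gives 80.8% power, and 35 per group gives more than 99.9%.

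**Reading 1: enrolled means randomised.** 39 × 0.9 = 35.1 evaluable per group, so pain power is 80.8%. Exclusions at surgery only raise the number who must be consented. The abstract, Study Design and Statistical Procedures all agree.

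**Reading 2: 78 is a cap on consents.** Let q be the proportion excluded at surgery. The document gives no value, so q is an assumption shown over a range. Evaluable per group = 78 × (1 − q) × 0.9 / 2, not rounded. Consents needed to randomise 78 = 78/(1 − q), rounded up.

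| q (assumed) | Randomised | Evaluable per group, 10% drop-out | Pain power | Pain power, no drop-out | Consents to randomise 78 |
|---|---|---|---|---|---|
| 0% | 78 | 35.1 | 80.8% | 84.8% | 78 |
| 3% | 75.7 | 34.1 | 79.6% | 83.7% | 81 |
| 5% | 74.1 | 33.3 | 78.7% | 82.9% | 83 |
| 10% | 70.2 | 31.6 | 76.4% | 80.8% | 87 |
| 15% | 66.3 | 29.8 | 74.0% | 78.5% | 92 |
| 20% | 62.4 | 28.1 | 71.3% | 75.9% | 98 |

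Even under a cap, a shortfall is not automatic. Keeping 35 per group (70 in all) allows 78 − 70 = 8 losses in total, before or after randomisation. With q = 10% and no later drop-out, power is still 80.8%. With 5% lost at each stage, 78 × 0.95 × 0.95 / 2 = 35.2 per group remain and power is about 80.9%. The urinary score keeps about 99.9% power even at 28 per group.

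**The case for a change.** The best argument for amending the text is that the consent reading is a natural one. In Study Design the number enrolled is followed at once by the sentence on informed consent, and nothing says that recruitment continues until 78 have been randomised. Study staff or an ethics board could take 78 as the consent ceiling. If enrolled does mean randomised, the protocol gives no number to be consented. A clarifying sentence would cost little and would leave the number treated unchanged.

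Part of this stands. The term is undefined, some consented patients may well not be randomised, and the drop-out allowance leaves nothing for them. But a wording that could be misread is not a plan that fails. No sentence stops accrual at 78 consents, and the sample-size section says outright how many will be randomised. The rule that certain patients are excluded and not randomised itself implies that more patients may be consented than randomised. The upper end of the exclusion range also has no support in the document, since eligibility already requires a planned stent and unilateral surgery and rules out ureteral stricture and a preoperative indwelling stent.

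**Conclusion.** The concern does not call for a change. The sample-size arithmetic is correct, and a team that follows Statistical Procedures as written randomises 78 patients and has about 80.8% power for pain after the planned drop-out. The claim that the plan cannot reach its target holds only if enrolled means consented and 78 is a hard ceiling; the document says neither.

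If both were true and the full 10% drop-out also occurred, pain power would be 78.7% at an assumed 5% exclusion, 76.4% at 10%, 74.0% at 15% and 71.3% at 20%. At 5% that is 1.3 points below target, which is small beside the uncertainty in an effect size taken from a meta-analysis of a different drug class. The urinary symptom score is not threatened on any of these assumptions. What is left is a missing definition, which the trial team can fill sensibly by counting the 78 at randomisation.

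### The sole adverse-event outcome counts only drug-related effects, with no assessor, causality criteria or index drug stated and no all-event comparison by arm

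*Combined protocol and SAP*

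**What the plan says.** The outcome list in STUDY DESIGN includes "v) drug-related adverse effects; (vi) other domains of the USSQ", and Research Aims & Abstracts lists the same outcome. No other adverse-event outcome appears.

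Two sentences in STUDY DESIGN describe collection. The paragraph on reporting at stent removal says "Patients will also be asked about drug-related adverse effects". It then adds: "The clinical research coordinator will contact patients every 2-3 days to assess for side effects". Neither gives an assessor, causality criteria, a severity scale or the drug to which an effect must be related.

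The same section sets out the other drugs a patient may be taking:
- Study drug: "Group A will receive fexofenadine 180 mg once daily in addition to standard of care treatment", with placebo in Group B.
- NSAIDs, as routine postoperative care.
- Narcotics: "If patients require further pain medication, narcotics will be considered on a limited basis".
- Anticholinergics: "Anticholinergic medications may also be prescribed in the postoperative period for patients with significant bother by urinary urgency and frequency".
- Alpha blockers, continued in chronic users.

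A separate secondary outcome, "iv) number of emergency department visits", carries no restriction by cause. STATISTICAL PROCEDURES offers only the general rule of t-tests for continuous and chi-square tests for nominal variables.

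**The concern.** Outcome (v) applies a causal filter before anything is counted. In these patients a new complaint could come from the anaesthetic, the ureteroscopy, the stent or any of up to five drug types. The Background itself attributes urgency, frequency, flank pain, hematuria, dysuria, sexual side effects and emotional distress to stents, so a study-drug effect resembling one of these could easily be assigned to the stent and lost. Conversely, because the index drug is not named, an effect of a narcotic or anticholinergic is drug-related on a literal reading and could be counted. Rescue use follows randomisation and may differ by arm if the study drug works.

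What is at stake is the tolerability statement. The Background cites the potential side effects of existing medications as part of the rationale, so readers will want a clear comparison of tolerability between the arms.

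**Working it through.** **1. Arm size available (reproduces the plan's figure).** Inputs from STATISTICAL PROCEDURES: pain-score difference 7.2, SDs 10.1 and 10.9, two-sided 0.05, power 80%, dropout 10%.
- Pooled SD = √((10.1² + 10.9²)/2) = 10.51; standardised difference = 7.2/10.51 = 0.685.
- The noncentral t solution is 34.4, rounded up to 35 per group (power 80.7% at 35). Dropout: 35/0.90 = 38.9, rounded up to 39.

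Both figures agree with the plan. They concern the pain score; the plan gives no figure for adverse effects.

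**2. What filtering can do (assumed rates, none from the documents).** Let b be the risk of an event not caused by the study drug, e the risk the study drug adds, s the share of study-drug events called related, and f the share of background events called related. Risks are treated as additive.
- All events: active b + e, placebo b.
- Filtered: active fb + se, placebo fb. The observed difference is se.

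Power is the normal approximation for two proportions at 35 per arm, two-sided 0.05. With b = 20% and e = 20 points:

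| Count | Active v placebo | Difference | Power |
|---|---|---|---|
| All events | 40% v 20% | 20 points | 45% |
| Filtered, s = f = 50% | 20% v 10% | 10 points | 21% |
| Filtered, s = 90%, f = 20% | 22% v 4% | 18 points | 61% |

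Over b = 10% to 30% and e = 10 to 30 points, power runs from 14% to 84% for all events, 8% to 47% with s = f = 50%, and 23% to 90% with s = 90% and f = 20%. So the filter can dilute or sharpen the contrast, depending on attribution rules the protocol does not give.

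**3. Rescue-drug effects (assumed rates).** Suppose true risks of 30% active and 15% placebo, plus 10 points of rescue-drug effects in the placebo arm only.
- All events: 30% v (15 + 10)% = 30% v 25%. The 15-point excess shrinks to 5.
- Filtered, half of every kind of event called related: 15% v (15 + 10)/2 % = 15% v 12.5%, a difference of 2.5 points.

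Counting all events therefore does not remove rescue-drug effects; they have to be shown separately.

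**The case against.** The strongest reply is that the gap is narrow and partly covered. The coordinator's contacts ask about side effects without the drug-related qualifier, emergency department visits are counted whatever the cause, and analgesic and anticholinergic use is recorded. Patients and the treating urologist are blinded, so error in attributing a given event should be similar in both arms and mainly add noise. Some restriction is also defensible here: an open question will pick up the very stent symptoms the drug is meant to reduce.

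Much of this stands. The contacts provide the opportunity to collect all events but do not define doing so, since a side effect is itself a causal notion. Emergency visits miss effects that do not lead to one. The blinding argument covers attribution of like events but not unequal rescue use; it also assumes blinding holds, while the coordinator's blinding is unstated and Research Aims & Abstracts calls the trial both double-blind and open label. The point about stent symptoms is right and shapes the fix: if the drug works, those symptoms will differ by arm.

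Two stronger readings are tempting. One is that patients themselves judge relatedness; the text says only that they are asked, and leaves the assessor unstated. The other is that the filter could reverse the comparison, for example to 15% v 17.5% in step 3. That needs half of study-drug and background events to be dropped while every rescue-drug event is kept (7.5% + 10% = 17.5%). Nothing in the documents supports that asymmetry, and treating all events alike gives 15% v 12.5%.

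**Conclusion.** The point holds as a gap in the definition of a secondary outcome. The sole adverse-event outcome is filtered on causality, with no assessor, criteria or index drug, and no all-event comparison by arm is planned. The comparison may be diluted or hard to interpret. Its error cannot be sized or given a direction, because every event rate, attribution share and rescue-drug effect used above is an assumption. The documents do not show directional bias.

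**What to change.** Redefine outcome (v), in both places where it is listed, as all adverse events from first dose of study drug to the follow-up visit, compared by randomised arm whatever the suspected cause. Specifically:

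- Ask one neutral question about any new problem at the planned coordinator contacts and the stent-removal visit, and repeat it at the follow-up visit so that the whole window is covered. Record onset date and severity.
- Tabulate the expected stent symptoms that the USSQ is there to measure (urgency, frequency, flank pain, hematuria, dysuria) separately from other events, because they may differ by arm through efficacy.
- Keep relatedness as a secondary description, judged blind to allocation and naming the suspected drug.
- Show the already tracked NSAID, narcotic and anticholinergic use by arm beside the events.

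The cost is a change of wording, a short contact script and a few recorded fields; no visit or call is added. The downside is more recorded events due to surgery, stent or rescue drugs.

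### Do the two wordings of secondary outcomes (i) and (ii), with duration and the counting window undefined, call for a change to the plan?

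*Combined protocol and SAP*

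**What the plan says.** Secondary outcomes are listed twice in the Combined protocol and SAP. Research Aims & Abstracts has "i) number of office phone calls due to urinary symptoms; (ii) duration of analgesic use"; the last paragraph of STUDY DESIGN has "i) number of office phone calls due to urinary symptoms and pain; (ii) duration of NSAID use". Items (iii) to (vi) and the two primary outcomes (USSQ urinary symptom score and pain score) agree in substance.

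STUDY DESIGN also describes treatment and data collection. NSAIDs are the routine postoperative analgesic, and "This treatment will be modified as needed on an individualized basis based on contraindications to these medications". Narcotics may be added on a limited basis, with the amount tracked. On records: "Patients will be asked to keep a record of their analgesic usage", and "At the time of stent removal, patients will also report their usage of NSAIDs, anticholinergics, and narcotics". The research coordinator contacts patients every 2-3 days, partly to see that medication logs are kept. On the stent: "The timing of ureteral stent removal will be determined based on physician and patient preference and will routinely be 1-2 weeks after surgery". A follow-up visit comes after removal.

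STATISTICAL PROCEDURES says only that "t-tests will be used for continuous variables, and chi-square tests will be used for nominal variables". No section defines duration, and none gives a start or end for counting calls or emergency department visits.

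**The concern.** The two lists are both current text and do not describe the same variables. A call about pain with no urinary complaint counts in one list only. A patient whose NSAID treatment is modified because of a contraindication could have days of analgesia that are not NSAID days, so NSAID duration and analgesic duration can differ for the same person. Duration itself could mean the number of days with any use or the last day of use. Calls and emergency visits could be counted to stent removal or to the follow-up visit.

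If nothing settled these choices, more than one result could be reported as the planned outcome (i) or (ii), and the choice might be made after the results were seen. That would weaken the secondary findings, though not the primary ones.

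**Working it through.** **1. Outcome (ii): which text fits the rest of the protocol?**

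| | Research Aims & Abstracts | STUDY DESIGN |
|---|---|---|
| Outcome (ii) | duration, any analgesic | duration, NSAIDs |
| Outcome (iii) | duration and quantity, narcotics | the same |
| Do (ii) and (iii) overlap? | yes, if narcotics count as analgesics | no |
| Match with the report at stent removal (NSAIDs, anticholinergics, narcotics) | no single matching category | NSAIDs give (ii), narcotics give (iii) |

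The design version is consistent with the data collected and keeps (ii) and (iii) separate. The abstract is also the looser text elsewhere: it calls the trial both double-blind and open label, while STUDY DESIGN describes a double-blind, placebo-controlled trial. The abstract's "ii) duration of analgesic use" reads as shorthand that was not brought into line.

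**2. Outcome (i).** The design text counts calls for urinary symptoms and for pain. These are the two symptom domains that form the primary outcomes, so the fuller wording is coherent with the trial's aims.

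**3. Window.** For medication, use is reported at stent removal, which implies a period from surgery to removal. For calls and emergency visits nothing is stated. Allocation is randomized 1:1 and blinded to patient and urologist, so either period (to removal or to follow-up) gives a fair comparison if it is used alike in both arms.

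**4. Duration.** The patient log, checked every 2-3 days, should allow either days with use or last day of use to be derived. A two-sample t-test of either one is a valid comparison of arm means.

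**5. Does any planned figure depend on this?** The only computed figure is the sample size. Inputs from STATISTICAL PROCEDURES: pain difference 7.2, SDs 10.1 and 10.9, two-sided alpha 0.05, power 80%, drop-out 10%.

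- Pooled SD = √((10.1² + 10.9²)/2) = √110.41 = 10.51
- Standardized difference = 7.2/10.51 = 0.685
- Noncentral t solution: n = 34.42, rounded up to 35 per group (power 0.807 at 35)
- Drop-out: 35/(1 − 0.10) = 38.9, rounded up to 39 per group; 2 × 39 = 78
- Urinary score: pooled SD = √((5.6² + 6.2²)/2) = 5.91; difference 8.4; n = 8.84, rounded up to 9 per group

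The stated 35, 39 and 78 reproduce. They use only the primary scores, so no choice of wording for (i) or (ii) alters them.

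**The case for a change.** The strongest contrary case is that the readings can give different answers. The documents supply no usage rates, so this can be shown only on assumed inputs: 35 per arm, stent 7-14 days, analgesic need ending after a mean of 5 days, 40% taking a narcotic, 10% on a non-NSAID substitute, and duration taken as last day of use. If the drug halves all analgesic durations, simulated power is 62.6% for NSAID duration and 81.7% for any analgesic, and the two disagree on significance in 22.4% of trials. With no drug effect, each alone rejects about 5%, and at least one of the two rejects 7.8%.

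It stands that the outcomes differ and that one definition must be used. The size does not stand as a finding about this trial:

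- The gap depends heavily on the assumed substitute share. At zero, power is about 74% against 82%, with about 10% disagreement.
- The order depends on the assumed effect. If only NSAID duration is halved, it reverses: 61.8% against 53.6%.
- Calls behave the same way. With 0.5 urinary and 0.5 pain calls assumed per patient, halving both gives 39.6% (urinary) against 67.6% (urinary and pain); halving only urinary calls gives about 39% against 20%.
- The 7.8% supposes that both definitions are tested and the favourable one reported, which nothing in the plan suggests.

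Neither wording is therefore statistically better. Variable stent time adds nothing: randomization balances it in expectation, and the documents show no difference between arms.

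One practical point remains. The report at removal names no analgesic class beyond NSAIDs and narcotics. Under the design text this does no harm to (ii), because a patient taking no NSAID simply has zero NSAID days, and the analgesic log covers other drugs.

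**Conclusion.** This is a clerical mismatch between an abstract and the design section, together with definitions that an analyst would ordinarily settle before unblinding. Following STUDY DESIGN gives sound secondary results: calls for urinary symptoms and pain, NSAID duration, and narcotic use kept separate. The meaning of duration, and the counting period for calls and emergency visits, can be fixed in the analyst's variable definitions from data already planned. Bringing the abstract into line is housekeeping.

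The effect on the primary analysis, the tests and the sample size is nil. For the secondary outcomes the documents support no numerical estimate of any effect. The conclusion rests on two assumptions: that the design section takes precedence over the abstract, which the collection text supports but does not state, and that one definition is chosen before unblinding and applied alike to both arms. No better method or corrected figure is at issue, so no change to the plan follows.
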